Men and women undergoing radiation therapy for lung cancer and other cancers in the chest at the Milwaukee VAMC and the Baltimore VAMC are eligible. Subjects will be recruited to this phase 2 trial after their diagnosis of cancer and after referral to Radiation Oncology for treatment. The existence of this study will be posted in the Radiation Oncology clinics. Subjects who require radiation therapy to attempt to cure or to palliate their disease will be eligible for this study. Subjects eligible for surgical resection and who do not need radiation therapy will not be eligible for this study. Subjects already on ACE inhibitors, angiotensin blockers, or renin antagonists will be excluded, but may participate if these medications are stopped by their treating physicians before the start of their participation in this study. Subjects with past history of allergy to ACE inhibitors will be excluded. Use of other antihypertensives is not an exclusion criterion. There will be no inclusion or exclusion by race or ethnic origin. Women and minorities are eligible. Children are not eligible because children do not develop lung cancer. Previous surgery and past or current use of chemotherapy are not exclusions. Subjects will have a Karnofsky performance status ≥ 70 , absolute neutrophils $> 1000/\text{mm}^3$, platelets $> 75,000/\text{mm}^3$, and hematocrit $> 25\%$. Liver and kidney function tests will be within normal range, alkaline phosphatase up to 1.2 and serum creatinine up to 1.1 times upper limit of normal, and baseline blood pressure will be systolic $> 110 \text{ mmHg}$ sitting. Pregnant or nursing subjects are excluded and fertile patients must have a negative pregnancy test and will use contraception. Lung function tests including spirometry, lung volumes and diffusing capacity will be obtained as part of standard of care for patients prior to radiotherapy, but indices from lung function tests will not be a cause for exclusion.

6. SUBJECT POPULATIONS. Indicate the subject populations to be recruited for the study.

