Dichotomous variables will be compared by chi-square, or Fisher's exact test, as indicated. Continuous variables will be compared by parametric or non-parametric statistics, as appropriate. Repeated measurements on the effects of enalapril and placebo on [RAS components] will be tested by a repeated measures ANOVA for continuous [RAS component] values and by a logistic type regression models [using GEE techniques for discrete [RAS component] values. In either case appropriate generalized linear models methods will be used to account for the association between repeated measurements over time on the testing procedure.] We will repeat the analysis using an appropriate regression analysis to account for possible patient factors which may influence outcome in addition to enalapril. We will also look at a model for RP and fibrosis using enalapril use and the RAS components as predictors as well as interactions between drug use and these predictors. Correlations will be made using Spearman's or Kendall correlation, as indicated. Dose modification factors (DMF) for the use of enalapril compared to placebo will not be tested since the expected radiation dose ranges will be too narrow. A more formal attempt to understand the mechanism of enalapril action on RP and fibrosis and determine if this is possibly derived through any one of the [RAS components] will use a structural equation modeling approach. This approach uses a matrix of regression coefficients from a series of regression models [of intermediate effects at the various time points to other intermediate effects at the same time point or to future intermediate or terminal effects. Using these coefficients and a postulated causal diagram which depicts which effects may be dependent on the patient history at a given time]. A final causal diagram which shows the relationship between drug, intermediate outcome and RP and or fibrosis [is constructed]. Path analysis techniques to construct the causal diagram can be constructed using the program DIGRAM (53). [This cited reference shows how this approach works by looking at causal factors for heart disease using data on behavioral factors measured at epochs in time.]

Survival analysis for aim 3

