Cancer-related survival and cancer recurrence will be compared for the enalapril and the placebo groups using Kaplan-Meier statistics. [We have calculated our ability to detect significant changes in cancer recurrence rates and in cancer survival, both for improvements in cancer-related outcomes and for adverse trends. We will be able to detect significant increases in recurrence rates or mortality. Our cohort of 162 subjects showed no difference in patient survival for those on ACE inhibitor compared to those not on ACE inhibitor. We do not

expect adverse changes in recurrence rates or patient survival. A mitigation benefit by enalapril could lead to an increase in patient survival, but less than a three month increase is not likely to be detected]

Recurrence rate change	Percent chance of detection
40 to 20 %	80%
40 to 60 %	81%

Cancer median survival change, months	Percent chance of detection
18 to 21	11%
18 to 12	60%

[There are potential pitfalls in the recurrence and survival analyses. These include the effects of interim sampling for the safety analyses, and adjustments for patient and disease characteristics as well as missing data.] The interim masked safety analyses will use the O'Brien correction to take into account the multiple analyses. In our analysis of survival, we will compare the recurrence-free survival rates between the treatment arms of the study in two ways. First we will examine the rates of death or recurrence using a Cox model. In this model we will adjust for patient/disease characteristics such as site of treatment, gender, age, stage of disease at randomization, and radiation dosage. We will also compare the disease free survival probabilities at two years using techniques that we have published (52). This method allows us to deal with the partial information available in patients who do not have a potential follow-up time of two years. This approach, which is a censored data version of logistic regression, will allow us to adjust the comparisons for patient, disease, and treatment factors. We picked two years here since the empirical evidence is that the disease-free survival curves tend to flatten out at around 20 months.

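### The RP and fibrosis comparison should be stratified by or adjusted for planned radiation dose: entry admits curative and palliative radiotherapy, and aim 3 already uses dose

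*SAP*

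**What the plan says.** **Comparison of RP and fibrosis (SAP, Endpoint and RAS analyses).** "Dichotomous variables will be compared by chi-square" or Fisher's exact test. The analysis is then repeated "using an appropriate regression analysis to account for possible patient factors which may influence outcome in addition to enalapril". No covariates are listed. A further model for RP and fibrosis names enalapril, the renin-angiotensin components and their interactions.

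**Dose (same section).** Dose modification factors comparing enalapril with placebo "will not be tested since the expected radiation dose ranges will be too narrow".

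**Aim 3 (SAP, Survival analysis for aim 3).** The Cox model for death or recurrence adjusts for "site of treatment, gender, age, stage of disease at randomization, and radiation dosage".

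**Eligibility (Protocol, section 5).** "Subjects who require radiation therapy to attempt to cure or to palliate their disease will be eligible for this study". The population is "Men and women undergoing radiation therapy for lung cancer and other cancers in the chest". No dose or lung-volume criterion appears there.

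**Randomization (Protocol, section 9).** Cancer stage is the only stratum. Age, gender, histology and chemotherapy are left out because they have no consistent relation with RP. Radiation dose and treatment intent are not mentioned, so that reason does not cover them.

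**The concern.** RP and fibrosis are injuries caused by the radiation itself. The Protocol's Background ties them to dose when it says they limit how much curative irradiation can be given. A trial that mixes curative and palliative treatment of lung and other chest tumours may therefore contain subjects with quite different risks of the endpoint.

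The stated test ignores that difference. If dose predicts the endpoint, a crude comparison leaves the variation between dose groups in the error term, and a stratified or adjusted test removes it. The SAP plans to use dose for recurrence and death but does not name it for the radiation-injury endpoints. What is at stake is power and the width of the confidence interval, chiefly for the radiographic endpoints, where events are common.

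**Working it through.** **1. The plan's own figures.** For two proportions,

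n per arm = [z(α)·√(2·p̄·(1−p̄)) + z(β)·√(p1(1−p1) + p2(1−p2))]² / (p1−p2)².

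Radiographic RP, 50% against 25%, with p̄ = 0.375 and power 0.80:

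- One-sided 0.05: (1.645 × 0.6847 + 0.8416 × 0.6614)² / 0.0625 = 45.3, so 46. The unpooled form gives 44. The SAP states 45.
- Two-sided 0.05: (1.960 × 0.6847 + 0.8416 × 0.6614)² / 0.0625 = 57.7, so 58.

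Clinical RP, 11% against 2.2%: 96 to 98 one-sided and 122 to 124 two-sided, against the SAP's 97. The SAP does not state sidedness. The powers below are two-sided, so at the SAP's sizes they start below 80% for a reason unrelated to dose.

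**2. Inputs.** From the documents: 11% clinical RP cut by 80%; 50% radiographic RP halved with 45 per arm; 200 subjects in total; about 100 subjects for the radiographic endpoint (Protocol, section 4). Assumed: 1:1 allocation, two dose groups, the same relative effect in each, and these mixes, chosen to return the SAP's control rates:

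- Clinical: 30% low-dose. 0.3 × 2% + 0.7 × 14.9% = 11.0%.
- Radiographic A: 30% low-dose. 0.3 × 15% + 0.7 × 65% = 50%.
- Radiographic B: 40% low-dose. 0.4 × 10% + 0.6 × 76.7% = 50%.

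**3. Power.** Simulation of 40,000 trials per setting, two-sided 0.05, Mantel-Haenszel statistic without and with the two dose strata:

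| Endpoint | n per arm | Reduction | Crude | Stratified | Gain (points) |
|---|---|---|---|---|---|
| Clinical RP | 100 | 80% | 74.9% | 76.2% | 1.3 |
| Radiographic, A | 45 | 50% | 68.4% | 75.7% | 7.3 |
| Radiographic, B | 45 | 50% | 69.0% | 82.5% | 13.5 |
| Radiographic, A | 100 | 50% | 95.9% | 97.8% | 1.9 |
| Radiographic, B | 100 | 50% | 95.8% | 99.1% | 3.3 |
| Radiographic, A | 100 | 35% | 72.0% | 77.9% | 5.9 |
| Radiographic, B | 100 | 35% | 72.2% | 85.9% | 13.7 |

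At 45 per arm the ordinary Pearson chi-square is slightly more liberal (69.9% and 70.5%). Measured against it, the gains are 5.8 and 12.0 points.

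**4. A wider grid for clinical RP.** 100 per arm, low-dose share 25 to 50%, high-to-low risk ratio 2 to 10, 20,000 trials per setting:

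- 11% cut by 80%: 74–75% crude, 75–76% stratified.
- 20% cut by 60%: 70–71% crude, 70–75% stratified.
- 20% cut by 50%: 52–53% crude, 51–57% stratified.

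**5. Validity.** With no drug effect, the crude test in the step 3 mixes rejects in 4.4 to 5.8% of trials and the stratified test in 4.8 to 5.1%. In the step 4 grid the crude test rejects in 4.8 to 5.5%. The crude test is not biased by leaving dose out.

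**6. Fibrosis.** Not simulated. At the SAP's 90% rate there is limited room for a dose gradient: with 30% low-dose and every other subject affected, the low-dose rate is still (0.90 − 0.70)/0.30 = 67%.

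**The case against.** A reader might infer that the SAP deliberately sets dose aside for the RP and fibrosis endpoints. It does not. The too-narrow clause gives the reason for not estimating dose modification factors. A dose modification factor, in its usual meaning, is a ratio of doses giving equal effect and needs a dose-response curve in each arm; declining to estimate one does not exclude a covariate. The planned regression to "account for possible patient factors which may influence outcome in addition to enalapril" could include dose, and the aim 3 text itself counts radiation dosage among patient and disease characteristics. Dose is unnamed, not excluded. This part of the objection stands.

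A reader might also infer that the comparison is biased, or that the trial population spans a wide dose range. Step 5 rules out the first. In the assumed clinical mix, an imbalance of 13 points in low-dose share (about one trial in 20: 1.96 × √(2 × 0.3 × 0.7/100) = 0.127) would move the control-risk RP rate by 0.13 × 0.129 = 1.7 points against an 8.8-point effect. That is ordinary chance variation, already allowed for in the test's error rate. On the second, the available text gives no dose range or case mix: the eligibility makes a wide range plausible, but does not establish it. Nor do the documents rank dose among the causes of RP.

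Finally, stratification by stage may partly track treatment intent, and a halving of radiographic RP already has about 96% power if all 200 subjects are imaged. Both are fair and reduce the benefit. Neither removes it: the crude test does not use the stage strata, the Protocol cites about 100 subjects for the radiographic endpoint, and the SAP itself says the size of the effect is uncertain.

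**Conclusion.** The concern holds as a matter of precision. The stated test for RP and fibrosis is crude, the adjusted repeat has no covariate list, and dose is named only for aim 3 in a trial open to curative and palliative treatment. Under the assumed mixes, using dose gains about 1 to 2 points of power for clinical RP at the SAP's 11% rate, and at most about 5 at a 20% rate. For a halving of radiographic RP it gains about 7 to 14 points at 45 per arm and 2 to 3 points at 100 per arm. At 100 per arm it gains about 6 to 14 points if the reduction is 35%. These figures depend on low-dose shares and risks that the documents do not give; if dose hardly varies or hardly predicts the endpoint, the gain is close to zero. Separately, the statement that dose ranges are too narrow is unsupported in the available text and needs reconciling with section 5 of the Protocol. The change is worthwhile and cheap, but the trial's validity does not depend on it.

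**What to change.** In the SAP's Endpoint and RAS analyses section:

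- Make the between-arm comparison of clinical RP, radiographic RP and radiographic fibrosis a Mantel-Haenszel test stratified by planned radiation dose category, with categories fixed before unblinding. Alternatively, use a regression with planned radiation dose as one prespecified covariate. Keep the crude test as a supporting analysis.
- Use the planned dose as it stands at randomization. Study drug can start while radiotherapy is under way, so delivered dose could be affected by events after assignment.
- Either state the expected dose range that supports the dose modification factor sentence, or reword the sentence so that it agrees with eligibility.

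The cost is SAP wording, since aim 3 already needs the dosage. The downside is one more parameter or stratum where clinical RP events are few: 100 × 0.11 = 11 against 100 × 0.022 = 2.2 expected. Two dose categories, with an exact version of the stratified test if strata are sparse, keep this manageable.

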Cover page

Title: Mitigation of radiation pneumonitis and fibrosis

ClinicalTrials.gov Identifier: NCT01754909

Most recent IRB approval Nov 13, 2017

Protocol for “Mitigation of radiation pneumonitis and fibrosis”

Cohen VA 1531-01, CLIN-004-12S

Original from Oct 31, 2012 Registration packet, incorporating amendments through July 2015

Objective

This project will test the effect of enalapril, an angiotensin-converting-enzyme inhibitor, to mitigate radiation pneumonitis and fibrosis in veterans undergoing radiation therapy for lung cancer and other cancers in the chest. It is based on the hypothesis that human normal tissue radiation injury can be safely and effectively mitigated, and on our extensive studies of radiomitigation in experimental animals. Lung cancer is more common in veterans than in the general population; this project is highly relevant to the medical care of veterans.

Research design and methodology

Enalapril or placebo will commence after the start of irradiation in veterans undergoing radiation therapy for lung cancer and other cancers in the chest, and their effects on radiation pneumonitis and fibrosis will be compared as the primary outcome measure. Enalapril will be used rather than captopril, because enalapril is given in single daily doses. This is a prospective, double-blinded, randomized, placebo-controlled trial, in a secondary-tertiary care setting. Subjects will join this trial voluntarily, based on their planned radiotherapy for lung cancer, and it is planned to enroll 200 subjects over the five years of this study. The intervention of this study is the use of enalapril or placebo, which will be maintained for the lifetime of the study subject.

2. To test the mechanism of mitigation of radiation lung injury by enalapril.
 - a. Angiotensinogen, plasma renin activity, and angiotensin II will be measured as renin-angiotensin system markers in all subjects.
 - b. The effect of enalapril on each marker will be assessed, as compared to placebo.
3. To confirm that enalapril in this use does not adversely affect cancer treatment outcomes.
 - a. Cancer recurrence and death from cancer will be compared for the enalapril and placebo groups.

These studies will be done in men and women undergoing radiation therapy for lung cancer and other cancers in the chest. Enalapril, or identical-appearing placebo, will be started within a day

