to up to 30 days of the beginning of the radiation treatments. The effect of the enalapril or placebo will be tested by their effect to reduce grade 2 or greater clinical radiation pneumonitis, by their effect on the renin-angiotensin system markers angiotensinogen, plasma renin activity, angiotensin II, and their effect to reduce radiographic evidence of pneumonitis and fibrosis.

NARRATIVE SUMMARY - HUMANS

1. **PURPOSE.** Provide the purpose or objectives of the study. Do not indicate "N/A" for this category.

To test the benefit of enalapril, an angiotensin-converting-enzyme-inhibitor, to mitigate radiation pneumonitis and fibrosis in humans.

2. **SCIENTIFIC RATIONALE.** Provide the reasons for doing the study. Do not indicate "N/A" for this category.

This project will test the effect of enalapril, an angiotensin-converting-enzyme inhibitor, to mitigate radiation pneumonitis and fibrosis in veterans undergoing radiation therapy for lung cancer and other cancers in the chest. It is based on the hypothesis that human normal tissue radiation injury can be safely and effectively mitigated, and on our extensive studies of radiomitigation in experimental animals. Lung cancer is more common in veterans than in the general population; this project is highly relevant to the medical care of veterans.

3. **BACKGROUND.** Provide information from previous studies leading up to this study, either from your laboratory or from those of others. If this is a treatment study involving investigational drugs, devices, or therapies, standard treatment must be clearly identified. Do not indicate "N/A" for this category.

Lung cancer is an important health problem for veterans. It is more common in them than in the general population, and lung cancer survival is less in veterans. Radiation therapy for lung cancer is used in over half of the cases, and it can be followed by radiation pneumonitis and fibrosis. These add significant morbidity and mortality, and they limit the doses of curative irradiation. Standard treatments for radiation pneumonitis and fibrosis are very limited. Mitigation is a new approach, being the use of an agent after initial irradiation but before the expression of radiation injury.

Our studies in rats show significant mitigation of radiation pneumonitis and fibrosis by angiotensin converting enzyme (ACE) inhibitors.

Our recent clinical trial shows the mitigation of radiation nephropathy by the ACE inhibitor captopril.

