Cover page

Mitigation of radiation pneumonitis and fibrosis

ClinicalTrials.gov Identifier: NCT01754909

Most recent IRB approval Nov 13, 2017

Statistical methods plan

Power analysis for aim 1

For the RP endpoint, at an 11% rate of clinical RP, and an 80% mitigation effect, 97 subjects are needed per arm for type 1 error of 0.05 and a power of 0.80. The 11% and 80% figures are based on our retrospective studies. Only 49 are needed per arm for a baseline clinical RP rate of 20%. We plan for 200 subjects because there is variability in the rate of RP, and because we cannot be certain about the magnitude of efficacy of enalapril.

control	%difference	treatment	n/arm	total n
11%	50%	6%	306	612
11%	60%	4%	199	398
11%	70%	3%	136	272
11%	80%	2%	97	194
11%	90%	1%	70	140
20%	50%	10%	155	310
20%	60%	8%	101	202
20%	70%	6%	70	140
20%	80%	4%	49	98
20%	90%	2%	36	72

For a 50% radiographic rate of RP, and a halving of this by enalapril, 45 subjects are needed per arm.

50%	50%	25%	45	90
-----	-----	-----	----	----

50%	60%	20%	30	60
50%	70%	15%	21	42
50%	80%	10%	15	30
50%	90%	5%	11	22

For the radiographic fibrosis endpoint, at a 90% fibrosis rate, 29 subjects per arm would identify a 30% reduction in radiographic fibrosis at 6 or 12 months.

Endpoint and RAS analyses

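### Aim 3 estimates recurrence and cancer-related survival by Kaplan-Meier with no rule for other-cause deaths; absolute risks should be shown as cumulative incidence, and the cause-specific test kept

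*SAP*

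**What the plan says.** The Protocol (Research design and methodology, aim 3) sets the comparison: "Cancer recurrence and death from cancer will be compared for the enalapril and placebo groups". The SAP (Survival analysis for aim 3) names the method: "Cancer-related survival and cancer recurrence will be compared for the enalapril and the placebo groups using Kaplan-Meier statistics". It does not say how a death from another cause, or a death without recurrence, is handled. The pitfalls it lists for these analyses are interim looks, covariate adjustment and missing data. Neither document, in the text available for review, mentions competing risks, cumulative incidence or cause-specific hazards.

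The same section tabulates detection chances under "Recurrence rate change" (40 to 20%, 40 to 60%) and "Cancer median survival change, months" (18 to 21, 18 to 12). It then plans two analyses of a combined endpoint. For one it says: "First we will examine the rates of death or recurrence using a Cox model". The other compares disease-free survival at two years.

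Three statements bear on whether other-cause death may differ by arm:
- On radiation pneumonitis (RP) and fibrosis, the Protocol (3. BACKGROUND) says: "These add significant morbidity and mortality, and they limit the doses of curative irradiation".
- The SAP sizes aim 1 "at an 11% rate of clinical RP, and an 80% mitigation effect".
- The SAP says of survival: "A mitigation benefit by enalapril could lead to an increase in patient survival".

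**The concern.** Someone who dies of another cause can no longer recur or die of cancer. Kaplan-Meier with such deaths censored estimates the risk in a hypothetical population where nobody dies of anything else. It is not the share of subjects who have the event, and it lies above that share whenever competing deaths occur before later events.

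In many trials the excess is much the same in both arms. Here the drug is meant to reduce an injury that the Protocol describes as adding to mortality, so the excess may be larger on placebo. Aim 3 is meant to reassure that enalapril does no harm to cancer outcomes, and absolute risks by arm are what a clinical reader will take from it.

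**Working it through.** **1. The plan's own figure.** No figure in the SAP is disputed. The nearest is the 81% chance of detecting recurrence of 60% against 40%. With 100 per arm (200 in total, 1:1 allocation assumed), two-sided 0.05 and a pooled two-proportion test: SE under the null = √(2 × 0.5 × 0.5/100) = 0.0707; SE under the alternative = √((0.24 + 0.24)/100) = 0.0693; z = (0.20 − 1.96 × 0.0707)/0.0693 = 0.886; power = 81.2%. The row is reproduced.

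**2. Inputs.**
- From the SAP: 40% recurrence; 18-month median; RP rates of 11% and 20%; 80% mitigation.
- Assumed, because the documents are silent: 40% is a 24-month risk (the SAP gives it no time point); constant, independent hazards; background other-cause death of 5 or 15% at 24 months; RP fatality of 10 or 50%.

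**3. Formulas.** Let q be the net probability of other-cause death by 24 months, with cumulative hazards B = −ln(1 − q) for other death and A for recurrence.
- True risk (cumulative incidence) = A/(A + B) × (1 − e^−(A+B))
- 1-KM, other deaths censored = 1 − e^−A

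**4. Overstatement in one arm.** Solve for A so that the true risk is 40%.
- q = 5%: B = 0.0513, A = 0.5267. Check: 0.9112 × 0.4390 = 0.400. 1-KM = 40.9%, which is 0.9 points too high.
- q = 25%: B = 0.2877, A = 0.6047. Check: 0.6776 × 0.5903 = 0.400. 1-KM = 45.4%, which is 5.4 points too high.

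**5. Hidden between-arm difference.** Placebo q = background + RP rate × fatality. On enalapril the RP part is multiplied by 0.2. The recurrence hazard is the same in both arms, so 1-KM is the same in both. True placebo recurrence is 40.0% throughout.

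| RP rate | Fatality | Background | q placebo / enalapril | 1-KM, both arms | True recurrence, enalapril | Hidden difference (points) |
|---|---|---|---|---|---|---|
| 11% | 10% | 5% | 6.1 / 5.2% | 41.2% | 40.2% | 0.2 |
| 11% | 10% | 15% | 16.1 / 15.2% | 43.3% | 40.2% | 0.2 |
| 20% | 10% | 5% | 7.0 / 5.4% | 41.3% | 40.3% | 0.3 |
| 20% | 10% | 15% | 17.0 / 15.4% | 43.5% | 40.3% | 0.3 |
| 11% | 50% | 5% | 10.5 / 6.1% | 42.1% | 40.9% | 0.9 |
| 11% | 50% | 15% | 20.5 / 16.1% | 44.3% | 41.0% | 1.0 |
| 20% | 50% | 5% | 15.0 / 7.0% | 43.0% | 41.6% | 1.6 |
| 20% | 50% | 15% | 25.0 / 17.0% | 45.4% | 41.8% | 1.8 |

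In the last row 1-KM is 5.4 points too high on placebo (45.4 − 40.0) and 3.6 on enalapril (45.4 − 41.8).

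**6. Cancer death, only if the 18-month median is cause-specific.** 1-KM at 24 months = 1 − 2^(−24/18) = 60.3%. With hazard ln 2/18 per month in the same formula, the true risk is 59.0% at q = 5% and 53.6% at q = 25%. The overstatement is 1.3 to 6.7 points.

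**7. The test.** A log-rank test on recurrence with other deaths censored was simulated at 100 per arm, two-sided 0.05, 20,000 trials. Type 1 error was 0.050 in the first row of the table and 0.049 in the last. Power for net 24-month recurrence of 40 against 60% was 82% and 79% in those rows, against 83% with no competing deaths.

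**The case against.** The strongest reply is that the SAP promises a comparison. It does not say that other deaths are censored, or that the curves will be reported as absolute risks; the recurrence percentages are power inputs. That stands, and it is why the point is conditional on the usual practice.

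A reader might infer that the harm test is biased or underpowered, or that Kaplan-Meier and log-rank must be abandoned. The documents do not support this. A test that censors other deaths is a valid comparison of cause-specific hazards, and the simulation shows it nearly unaffected.

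A reader might also infer that the death-or-recurrence analyses share the fault. They do not. The Cox composite counts any death as an event, as disease-free survival conventionally does. They answer a different question, though. Event-free survival is e^−(A+B), so at equal recurrence hazards it is 0.5 to 4.6 points higher on enalapril across the table's rows, from fewer other deaths alone. They do not replace separate curves for recurrence and cancer death.

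On size, several objections stand:
- The upper end needs half of RP cases to be fatal, which no document states.
- The SAP also reports that survival in its 162-subject cohort did not differ by ACE-inhibitor use, so a difference in other-cause death is possible, not established.
- Sampling error is larger. At 100 per arm a 40% risk has a 95% interval of ±1.96√(0.24/100) = ±9.6 points, and a difference ±1.96√(0.48/100) = ±13.6.
- The 18-month median may be all-cause. Its row label refers to cancer, but the adjoining text speaks of patient survival and a three-month gain, which is the 18-to-21 row. If it is all-cause, step 6 falls away.
- Steps 4 and 6 are not one model. Recurrence of 40% beside cancer death of 54 to 59% would require cancer deaths without recurrence, which compete with recurrence too.

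**Conclusion.** The point holds for estimated and displayed absolute risks only. If other-cause deaths are censored, 1-KM overstates recurrence by about 1 to 5 points per arm, given 5 to 25% net other-cause death at 24 months, a 24-month reading of the 40%, and independent constant hazards. At equal recurrence hazards it hides a difference of 0.2 to 0.3 points at 10% RP fatality, and at most 1.8 points at 50%. The direction follows from the method; the sizes are assumptions. For cancer death a similar overstatement applies only if the 18-month median is cause-specific, which the SAP leaves ambiguous. The cause-specific test and the composite analyses stand. This is a cheap improvement in estimation and display.

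**What to change.** Amend the SAP's aim 3 section as follows:
- State that recurrence and cancer death are tested between arms on cause-specific hazards (log-rank or Cox, other deaths censored), and keep that test.
- Estimate and display the absolute risk of each by Aalen-Johansen cumulative-incidence curves. For cancer death the competing event is death from another cause. For recurrence it is any death without recurrence.
- Show other-cause and all-cause death by arm beside them.

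The cost is a few sentences, standard software, slightly more analysis and two more curves to report. No new data are needed, because the aim 3 endpoint of death from cancer already requires cause of death.
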